6.1.2. Sensitivity/Supplementary Analyses

Supplemental analyses will be performed for the primary efficacy endpoint:

- 1. An analysis of the primary endpoint will be conducted excluding data after the date of non-study antiviral or monoclonal antibody start for participants that received non-study antiviral or monoclonal antibody therapy post-baseline (between randomization and Day 44) for the treatment of COVID-19.
- 2. An analysis of the primary endpoint will be conducted to include all NP swab SARS-CoV-2 RNA data regardless of whether participants received non-study antiviral or mAb treatment post-baseline (between randomization and Day 44) for the treatment of COVID-19.
- 3. An analysis of the primary endpoint will be conducted where participants with baseline SARS-CoV-2 RNA level <LLOQ will be excluded.
- 4. An analysis of the primary endpoint will be conducted where participants who do not meet the protocol-defined immunocompromised criteria will be excluded.
- 5. An analysis of the primary endpoint will be conducted excluding participants from site 1030.

6.2. Secondary Endpoint(s)

6.2.1. Time to first NP swab SARS-CoV-2 RNA<LLOQ (<2.0 log10 copies/mL) for participants with NP swab SARS-CoV-2 RNA ≥LLOQ at baseline

6.2.1.1. Main Analysis

Time (days) to first NP swab SARS-CoV-2 RNA<LLOQ (<2.0 log₁₀ copies/mL) will be evaluated for participants with NP swab SARS-CoV-2 RNA \geq LLOQ at baseline. The first day of NP swab SARS-CoV-2 RNA<LLOQ will be considered the First Event Date. Time

DMB02-GSOP-RF02 7.0 Statistical Analysis Plan Template 31-Jan-2022 PFIZER CONFIDENTIAL TMF Doc ID: 98.03 Page 17 of 32 (days) to first NP swab SARS-CoV-2 RNA<LLOQ will be calculated as (First Event Date) – (First Dose Date) +1.

There are limitations to the timing of the first event date as NP viral RNA is generally only captured at in-person scheduled visits during the study.

The Day 44 visit day is the last possible day the NP swab SARS-CoV-2 RNA<LLOQ can be achieved.

For a participant that either completes the Day 44 visit of the study or discontinues from the study before the Day 44 visit without NP swab SARS-CoV-2 RNA<LLOQ (censored), censoring date will be at the last date on which NP swab SARS-CoV-2 RNA is assessed, and time will be calculated as (Censoring Date) – (First Dose Date) +1 or the Day 44 visit whichever occurs first.

Time to NP swab SARS-CoV-2 RNA<LLOQ will be summarized graphically using Kaplan-Meier plots for each of the treatment groups in main study population.

6.2.2. Time to sustained NP swab SARS-CoV-2 RNA <LLOQ (<2.0 log10 copies/mL) through Day 44 for participants with NP swab SARS-CoV-2 RNA ≥LLOQ at baseline

Time (days) to sustained NP swab SARS-CoV-2 RNA<LLOQ (<2.0 log₁₀ copies/mL) will be evaluated. Sustained is defined as NP swab SARS-CoV-2 RNA level not \geq 2.0 log₁₀ copies/mL at any study visit (through Day 44) following the first study visit where the participant's NP swab SARS-CoV-2 RNA <LLOQ.

Let *t* represent the number of days between 5 and 35 inclusive for which there is a protocol-specified measurement of SARS-CoV-2 RNA level on Day *t*.

Then a sustained event will correspond to the first possible value of *t* to satisfy the following criteria:

- a) The Day 44 SARS-CoV-2 RNA level is <LLOQ
- b) The Day t SARS-CoV-2 RNA level is <LLOQ
- c) All available (non-missing) protocol-specified SARS-CoV-2 RNA measurements between Day *t* and Day 44 are <LLOQ
- d) No more than one of the protocol-specified SARS-CoV-2 RNA measurements between Day *t* and Day 44 are missing.

There are limitations to the timing of the first event date as NP viral RNA is generally only captured at in-person scheduled visits during the study.

The Day 35 visit is the last possible day the sustained NP swab SARS-CoV-2 RNA<LLOQ can be achieved.

DMB02-GSOP-RF02 7.0 Statistical Analysis Plan Template 31-Jan-2022 PFIZER CONFIDENTIAL TMF Doc ID: 98.03 Page 18 of 32 The time to the sustained event is defined as:

- For a participant with sustained event at Day *t*, the First Event Date is the date of the Day *t* measurement, and time to event will be calculated as (First Event Date) (First Dose Date) +1.
- For a participant for which no possible value of *t* ≤ the 35 visit satisfies the criteria for a sustained event (censored), censoring date will be the date of the last available protocol-specified SARS-CoV-2 RNA measurement other than Day 44, and time will be calculated as (Censoring Date) (First Dose Date) +1.

Time to sustained NP swab SARS-CoV-2 RNA<LLOQ will be summarized graphically using Kaplan-Meier plots for each of the treatment groups in main study population.

6.2.3. Proportion of participants with SARS-CoV-2 RNA <LLOQ in plasma over time.

• The proportion of participants with SARS-CoV-2 RNA <LLOQ as measured in plasma will be summarized at each study visit through week 24 for each treatment arm. In addition, 95% CIs for the proportion of participants with SARS-CoV-2 RNA <LLOQ in plasma at each study visit will be calculated for each treatment arm.

6.2.4. Proportion of participants with SARS-CoV-2 RNA level in NP swabs <2.0 log₁₀ copies/mL at each study visit

The proportion of participants with SARS-CoV-2 RNA < 2.0 log₁₀ copies/mL as measured by NP swab will be summarized at each study visit through Week 24 for each treatment arm. In addition, 95% CIs for the proportion of participants with SARS-CoV-2 RNA <2.0 log₁₀ copies/mL as measured by NP swabs at each study visit will be calculated for each treatment arm.

6.2.5. Change from baseline in SARSCoV-2 RNA level in NP swabs and in plasma over time.

Descriptive statistics by treatment group for the change from baseline to each study visit (Day 5, 10, 15, 21, 28, 35, 44) will be provided. Participants are excluded from the analysis for reasons of Not Detected, Zero or Missing baseline and/or post-baseline viral load results.

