## **Prohibited During the Study**

Use of a non-study antiviral or monoclonal antibody therapy for the treatment of COVID-19 within 15 days after randomization is prohibited, except for participants who progress to severe or critical COVID-19.

Nirmatrelvir and ritonavir are both primarily metabolized by cytochrome P450 (CYP) 3A4. In addition, ritonavir is a strong inhibitor of CYP3A4. Therefore, concomitant use of medications that are strong inducers of CYP3A4 and which are contraindicated in combination with nirmatrelvir/ritonavir (see [Appendix 8](#)) are prohibited during study treatment.

Additionally, coadministration of nirmatrelvir/ritonavir with other medications that are not contraindicated but are highly dependent on CYP3A4 for clearance may require dose adjustment or additional monitoring. Investigators should reference [Appendix 8](#) for a nonexhaustive list of these medications and consult the Pfizer medical monitor for guidance on coadministration with nirmatrelvir/ritonavir.

Medications or substances that are strong inducers of CYP3A4 and that are contraindicated in combination with nirmatrelvir/ritonavir must be discontinued for an appropriate washout period prior to the first dose of nirmatrelvir/ritonavir and are prohibited for the duration of the study treatment period and for 4 days after the last dose of nirmatrelvir/ritonavir ([Appendix 8](#)). The appropriate washout period for CYP3A4 inducers should be determined based on the prescribing information for the concomitant medication and in consultation with the medical monitor.

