2.2.2. Secondary Estimand(s)

Not Applicable.

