6.1.1. Main Analysis

The primary descriptive analysis will summarize, separately for the main study population and the population with rebound, the number and proportion of participants with sustained NP swab SARS-CoV-2 RNA <LLOQ (defined as <2.0 log₁₀ copies/mL) from Day 15 through Day 44 for each treatment arm in the Evaluable Analysis Set and FAS. Participants DMB02-GSOP-RF02 7.0 *Statistical Analysis Plan Template* 31-Jan-2022

> PFIZER CONFIDENTIAL TMF Doc ID: 98.03 Page 16 of 32

receiving non-study antiviral or monoclonal antibody therapy post-baseline (between randomization and Day 44 visit) for the treatment of COVID-19 will be considered as not achieving sustained NP swab SARS-CoV-2 RNA <LLOQ in the primary analysis.

As viral load measurements from NP swabs are taken on Days 15, 21, 28, 35, and 44 during the time interval from Day 15 to Day 44, all of the measurements that are non-missing must be <LLOQ (including undetectable), and the Day 15, Day 44, and no more than one of the Day 21, 28, and 35 measurements can be missing in order for the event to be considered sustained.

In addition, 95% CIs for the proportion of participants with sustained NP swab SARS-CoV-2 RNA <LLOQ from Day 15 through Day 44 for each treatment arm will be calculated using binomial distribution normal approximation. The difference in proportions for the primary endpoint and associated 95% CI will be calculated for each pairwise comparison of the treatment arms.

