8. APPENDICES

Endpoint	Analysis Type	Population	Data Inclusion and Rules for Handling Intercurrent Events and Missing Data	Analysis Model
Proportion with sustained SARS- CoV-2 RNA < LLOQ from Day 15 to Day 44 (NP)	Primary	Evaluable, FAS	Intercurrent event: non-study anti- viral or mAb therapy – participant considered failure No imputation of missing data	Descriptive (n, %), 95% CI for proportion and the difference in proportion using binomial distribution normal approximation
Proportion with sustained SARS- CoV-2 RNA < LLOQ from Day 15 to Day 44 (NP)	Supplementary	Evaluable	Intercurrent event: non-study anti- viral or mAb therapy – data excluded/considered missing No imputation of missing data	Descriptive (n, %), 95% CI for proportion and the difference in proportion using binomial distribution normal approximation
Proportion with sustained SARS- CoV-2 RNA < LLOQ from Day 15 to Day 44 (NP)	Supplementary	Evaluable	Intercurrent event: non-study anti- viral or mAb therapy – data included as is No imputation of missing data	Descriptive (n, %),95% CI for proportion and the difference in proportion using binomial distribution normal approximation
Proportion with sustained SARS- CoV-2 RNA < LLOQ from Day 15 to Day 44 (NP)	Supplementary	Evaluable	Participants with baseline SARS- CoV-2 RNA level <lloq be
excluded Intercurrent event: non-study anti- viral or mAb therapy – participant considered failure</lloq>	Descriptive (n, %), 95% CI for proportion and the difference in proportion using binomial distribution

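### Time to sustained clearance (and, less often, time to first clearance) counts clearance after a non-study antiviral or antibody as an event, while the primary endpoint counts the rescued participant as a failure

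*SAP*

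**What the plan says.** **Primary endpoint.** SAP 6.1.1 provides that a participant given a non-study antiviral or monoclonal antibody for COVID-19 between randomization and the Day 44 visit "will be considered as not achieving sustained NP swab SARS-CoV-2 RNA <LLOQ in the primary analysis". The primary row of SAP Appendix 1 repeats this as "participant considered failure". SAP 6.1.2 adds two supplementary versions of the primary: one drops data after rescue starts, the other keeps all data.

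**Time to first clearance (SAP 6.2.1).** "The first day of NP swab SARS-CoV-2 RNA<LLOQ will be considered the First Event Date". Participants without the event are censored at their last swab, at most at the Day 44 visit.

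**Time to sustained clearance (SAP 6.2.2).** "Then a sustained event will correspond to the first possible value of" t, between Day 5 and Day 35, that meets criteria (a) to (d). Those criteria concern the Day 44 value, the Day t value, "All available (non-missing) protocol-specified SARS-CoV-2 RNA measurements between Day" t and Day 44, and the number of missing visits. Censoring is at the last available measurement other than Day 44.

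Neither section mentions rescue. The Appendix 1 rows for both endpoints give only a missing-data rule. Secondary estimands (SAP 2.2.2) are "Not Applicable". Protocol 9.3.3 leaves secondary definitions to the SAP.

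**When rescue can happen.** Protocol 6.9: "Use of a non-study antiviral or monoclonal antibody therapy for the treatment of COVID-19 within 15 days after randomization is prohibited", except on progression to severe or critical COVID-19. That prohibition does not reach the Day 21, 28, 35 and 44 swabs. Under Protocol 7.1, participants who stop study drug stay in follow-up.

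**The concern.** The first secondary objective is the effect of treatment duration on the rate of sustained virologic clearance. It has two endpoints, and neither has a rescue rule or a rescue sensitivity analysis. Protocol 4.3 justifies longer treatment as a way to prevent viral RNA rising again after treatment ends. If that is right, rescue would tend to be more frequent after the shorter course. Counting clearance achieved with a non-study drug as an event would then raise the shorter-course curve and shrink the contrast that the study is meant to describe. A programmer following 6.2.1 and 6.2.2 has no basis for doing anything else.

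**Working it through.** **1. The plan's own figure.** The only design figure is Table 2. Half-width = 1.96 × √(p(1−p)/50) gives 0.083, 0.111, 0.127, 0.136 and 0.139 for p = 0.1 to 0.5. This reproduces Table 2, so the table's entries are half-widths although it labels them widths (a separate matter). The point here does not depend on them. For scale, the half-width for a difference between two arms of 50 is 1.96 × √(2p(1−p)/50) = 0.180 at p = 0.7 and 0.196 at p = 0.5.

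**2. The rules applied to example participants**, all with baseline at or above LLOQ.

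| Participant | Time to first | Time to sustained | Primary |
|---|---|---|---|
| A: at or above LLOQ on Days 5 and 10, rescue Day 12, below LLOQ Days 15 to 44 | Event, Day 15 | Event, Day 15 | Failure, solely because of rescue |
| B: first below LLOQ on Day 15, rebound Day 21, rescue Day 22, below LLOQ Days 28, 35 and 44 | Event, Day 15 (before rescue) | Event, Day 28 | Failure; the Day 21 swab alone suffices |
| C: at or above LLOQ through Day 15, rescue between the Day 15 and Day 21 swabs, below LLOQ from Day 21 | Event, Day 21 | Event, Day 21 | Failure; the Day 15 swab alone suffices |

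In all three, clearance after rescue is credited as a sustained event. Time to first is affected in A and C, where no swab was below LLOQ before rescue, and not in B. Only in A does the rescue rule by itself create the disagreement with the primary.

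**3. Size, under assumptions.** The documents give no rescue or post-rescue clearance rates. Suppose rescue is drawn from participants who would not otherwise clear, a fraction c of them clear by Day 35 and hold to Day 44, and nobody is censored before Day 35. Cumulative sustained clearance by Day 35 is then a simple proportion, and

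shift in the between-arm difference = (r₁ − r₂) × c.

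| Assumed rescue, 5-day vs 15-day | c = 0.5 | c = 1.0 |
|---|---|---|
| 5% vs 1% | 0.04 × 0.5 = 2 points | 4 points |
| 10% vs 2% | 0.08 × 0.5 = 4 points | 8 points |
| 15% vs 3% | 0.12 × 0.5 = 6 points | 12 points |

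A Kaplan-Meier check agrees. Take two arms of 50 with 20 unrescued clearers each, and 5 versus 2 rescued participants who all clear at Day 28. As written, the arms show 25/50 = 0.50 and 22/50 = 0.44, a 6-point difference. Under the primary's rule both show 20/50 = 0.40.

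**4. Direction.** Relative to the primary's rule, crediting can only add events. It can also hide a real deficit. With assumed unrescued clearance of 40% (5-day) and 48% (15-day), 10% versus 2% rescued and c = 1, the as-written figures are 0.40 + 0.10 = 0.50 and 0.48 + 0.02 = 0.50, so an 8-point difference disappears.

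**The case against.** Several points on the other side stand.

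- **A reader might infer that a participant who rebounds, is rescued and clears is classified differently because of the rescue rule.** The documents do not support that. SAP 6.1.1 requires every non-missing swab from Day 15 to Day 44 to be below LLOQ, so a rebound swab in that window fails the primary with or without rescue. Someone who clears late and unaided is also a primary failure and a sustained event. The endpoints are not twins: one has a fixed Day 15 start, the other a floating t from Day 5 to Day 35 and a restriction to baseline at or above LLOQ.
- **A reader might treat both endpoints as equally exposed.** A first clearance reached before rescue is untouched.
- **A reader might take 2 to 12 points as an estimate.** It is an illustration, and its upper end needs every rescued participant to clear.
- **Part of the issue is visible elsewhere.** The primary is analysed three ways (SAP 6.1.1 and 6.1.2), antiviral and antibody use is summarised by arm (6.4.4) and viral rebound is reported (6.2.6). These would show an imbalance in rescue, but not its effect on clearance after Day 15 or on either curve.
- **Using all swabs regardless of rescue is a legitimate treatment-policy strategy**, and the amendment log ties the regulatory request to the primary analysis. That is fair, but the SAP never states this strategy for the secondary endpoints, and for the primary it places the all-data version among the supplementary analyses.

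**Conclusion.** The point holds in a limited form. As written, SAP 6.2.2, and 6.2.1 when rescue precedes the first swab below LLOQ, counts clearance after rescue as an event. This follows from complete event and censoring rules that are silent on rescue, not from a sentence saying that such clearance counts.

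The consequence is conditional. A reader might infer that the analysis necessarily favours the arm with more rescue, but that requires rescue to differ between arms and rescued participants to clear afterwards, and the documents give no data on either. If both hold, the curve of the arm with more rescue is raised relative to the primary's rule and the contrast between durations can narrow. The illustrative shift of about 2 to 12 points is below the 18 to 20 point half-width for a difference with 50 per arm. The number analysed can be smaller than 50, given the baseline restriction and the exclusion of Site 1001 from efficacy analyses. The shift is systematic rather than random.

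These are descriptive Kaplan-Meier summaries with no planned test, so there is no type I error consequence. It is a cheap improvement, not a flaw that threatens the primary result.

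**What to change.** In SAP 6.2.1, 6.2.2 and the two matching rows of Appendix 1, state the strategy for non-study antiviral or antibody use, and present two sets of Kaplan-Meier curves.

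1. **Under the primary's rule.** For sustained clearance, any participant who starts such therapy for COVID-19 by the Day 44 visit is a non-event. For first clearance, a participant who starts it before the first swab below LLOQ is a non-event. Keep these participants in the risk set to the last possible event day (Day 35 for sustained, Day 44 for first). Do not censor them at rescue, because that censoring would be informative.
2. **As observed.** The curves as now specified, labelled as including all swabs regardless of rescue.

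The cost is SAP wording and one extra version of two plots; the rescue flag is already needed for the primary. There is also a substantive downside. A participant below LLOQ from Day 5 who starts an antiviral on Day 40 counts as not having sustained clearance, as already happens in the primary. The as-observed curves keep that participant's clearance visible.

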5.2.3. Analyses for Time-to-Event Endpoints

For time-to-event endpoints (eg, time to first NP swab SARS-CoV-2 RNA<LLOQ [<2.0 log_{10} copies/mL] for participants with NP swab SARS-CoV-2 RNA ≥LLOQ at baseline), Kaplan-Meier analysis where tabular summaries of the Kaplan-Meier curves providing the median and quartiles, will be provided for each treatment group. In addition, the Kaplan-Meier curves will be presented graphically.

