5.3. Methods to Manage Missing Data

For SARS-CoV-2 RNA data, samples producing a result of <LLOQ or undetectable will not be considered missing, but rather will be imputed using values of 1.7 [log₁₀(50)] or 0.0 log₁₀ copies/mL, respectively. Missing SARS-CoV-2 RNA data will not be imputed.

As all analyses are descriptive, missing endpoint data will result in a summary where the N for that endpoint (and time point) is smaller than the total N of the corresponding analysis set. No imputation of the missing data will be performed.

For safety data, missing and partial dates will be programmatically handled according to Pfizer standards.

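### Time to sustained clearance (SAP 6.2.2) counts participants lost while already <LLOQ as uncleared up to their last swab, so such losses pull the Kaplan-Meier clearance curve down even when they are unrelated to outcome

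*SAP*

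**What the plan says.** SAP 6.2.2 defines a sustained event at Day t, where t is a scheduled swab day from Day 5 to Day 35. Criterion (a) is "The Day 44 SARS-CoV-2 RNA level is <LLOQ". Criteria (b) and (c) require the Day t swab and every available swab from there to Day 44 to be <LLOQ. Criterion (d) reads "No more than one of the protocol-specified SARS-CoV-2 RNA measurements between Day" t and Day 44 are missing. The event is back-dated: "the First Event Date is the date of the Day *t* measurement". The latest possible event time is fixed: "The Day 35 visit is the last possible day the sustained NP swab SARS-CoV-2 RNA<LLOQ can be achieved".

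For everyone without an event, the "censoring date will be the date of the last available protocol-specified SARS-CoV-2 RNA measurement other than Day 44". The result of that swab plays no part.

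SAP 5.3 adds: "Missing SARS-CoV-2 RNA data will not be imputed". The output in 6.2.2 is Kaplan-Meier plots by arm in the main study population, and 5.2.3 promises "Kaplan-Meier analysis where tabular summaries of the Kaplan-Meier curves providing the median and quartiles, will be provided for each treatment group". SAP Appendix 2.1 assigns any swab from Day 40 to Day 49 to the Day 44 visit. The sensitivity and supplementary analyses in 6.1.2 cover the primary endpoint only.

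**The concern.** Kaplan-Meier estimation assumes that a participant in the risk set just before a visit is known not to have had the event, and that being at risk does not depend on what happens later. In 6.2.2 it does depend on it. Take two participants with identical swabs, both <LLOQ at Days 10, 15, 21 and 28. One attends Day 44, is <LLOQ and gets an event at Day 10. The other leaves after Day 28, can have no event, and is counted as at risk and uncleared at Days 10, 15, 21 and 28. Censoring at the last swab is sound for time to first clearance (6.2.1), where status is known at each swab. It is not sound for an event that can only be confirmed later.

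At stake is one of the two endpoints under the secondary objective on treatment duration and the rate of sustained clearance. Loss that differs between arms would appear as a difference between durations, and no planned analysis of this endpoint would show it for what it is.

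**Working it through.** The plan states no median, event count or dropout rate for this endpoint, so there is no figure to reproduce.

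**Inputs.** From the SAP: swabs at Days 5, 10, 15, 21, 28, 35 and 44 (6.2.5), the event and censoring rules of 6.2.2, and about 50 participants per arm (2.4). Assumed, because the documents give none:
- The share f whose sustained clearance starts at Days 5/10/15/21/28/35 is 15/25/25/15/8/4%, so the true cumulative proportion is 0.65 at Day 15 and 0.80 at Day 21.
- There is no rebound.
- A share w leaves at random, equally likely after any one of the six swabs from Day 5 to Day 35.

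**A ten-person case.** All ten are >=LLOQ at Day 5 and <LLOQ from Day 10. If nobody leaves, the Day 10 estimate is 10/10 = 100%. If two leave after a <LLOQ Day 21 swab, eight events occur among ten at risk, so the estimate is 80% and stays there to Day 35. If those two are instead censored at Day 5, their last visit >=LLOQ, it is 8/8 = 100%.

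**General formula.** Let F(t-) be the proportion cleared before t, F(t) the proportion cleared by t, and G(t) the share of leavers with a swab at or after t (1, 5/6, 4/6, 3/6, ...).
- No loss: hazard = f(t) / (1 - F(t-)).
- SAP rule: hazard = (1-w) f(t) / [(1-w)(1 - F(t-)) + w G(t)]. Every leaver still attending sits in the denominator, cleared or not, so the hazard is too low.
- Leavers whose last swab is <LLOQ censored at the last visit >=LLOQ: hazard = (1-w) f(t) / [(1-w)(1 - F(t-)) + w G(t)(1 - F(t))].

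SAP rule at w = 0.20:

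| Day | Hazard | Cumulative cleared | Truth |
|---|---|---|---|
| 5 | 0.120/(0.800+0.200) = 0.120 | 0.120 | 0.15 |
| 10 | 0.200/(0.680+0.167) = 0.236 | 0.328 | 0.40 |
| 15 | 0.200/(0.480+0.133) = 0.326 | 0.547 | 0.65 |
| 21 | 0.120/(0.280+0.100) = 0.316 | 0.690 | 0.80 |

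Changed censoring at w = 0.20: the hazards at Days 5, 10 and 15 are 0.120/0.970 = 0.124, 0.200/0.780 = 0.256 and 0.200/0.527 = 0.380, which gives 0.596 at Day 15. The Day 21 hazard is 0.120/0.300 = 0.400, which gives 0.758.

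Day 15 estimates (truth 0.650):

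| Random loss | SAP rule | Changed censoring | Only those with a Day 44 swab |
|---|---|---|---|
| 5% | 0.625 | 0.638 | 0.650 |
| 10% | 0.600 | 0.625 | 0.650 |
| 20% | 0.547 | 0.596 | 0.650 |

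**False differences between identical arms at Day 15.** Under the SAP rule, 5% vs 10% gives 0.625 - 0.600 = 2.5 points and 5% vs 20% gives 0.625 - 0.547 = 7.8 points. Under the changed rule, 5% vs 20% gives 0.638 - 0.596 = 4.2 points. For scale, the standard error of a difference at 50 per arm is sqrt(2 x 0.65 x 0.35 / 50) = 0.095, or 9.5 points.

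**Quartiles.** On nominal visit days the true upper quartile is Day 21 (0.80). At 20% loss the SAP rule gives 0.690 at Day 21 and 0.78 at Day 28, so the quartile moves to Day 28. The median stays at Day 15, because 0.547 still exceeds 0.5.

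**Rebound.** A separate simulation assumed 60% first <LLOQ by Day 15 and 15% later rebound. Day 15 sustained clearance was 0.51 with no loss, 0.49 at 5% and 0.43 at 20%, so the bias persists.

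**Loss while >=LLOQ.** These participants are censored at a swab where they were known to be uncleared. With all loss of this kind and the same main inputs, the SAP rule returned 0.650 at Day 15 for 5, 10 and 20%. The restricted curve was then too high: 0.729 against 0.650 at 20%.

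**The case against.** Requiring an observed Day 44 swab is part of what sustained through Day 44 means, and treating an unconfirmed participant as not shown to be sustained is cautious in a trial concerned with rebound. That stands for the event definition. It does not justify the censoring date. The rule neither counts the participant as a failure throughout nor drops them when status becomes unknown; it holds them as uncleared at visits where the swab was <LLOQ. SAP Appendix 1 states missing-as-not-cleared where it is wanted (the proportions <LLOQ over time) and lists no imputation for this endpoint.

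Several points limit the size, and they stand. Stopping study drug is not withdrawal (Protocol 7.1). Home and mobile visits can collect NP swabs (Protocol 8.1.2, 8.1.3). No hypothesis is tested (SAP 5.1). Disposition by arm (6.4.2) and the proportion <LLOQ at each visit (6.2.4) would put unequal loss in view, though not its effect on this curve.

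A reader might infer more than the documents support:
- That any withdrawal lowers the curve, so the arm with more withdrawal always looks slower. Only loss while <LLOQ does this. If those who leave while >=LLOQ would have cleared more slowly than those who stay, the bias can run the other way.
- That anyone leaving before Day 44 can never have an event. A swab on Day 40 to 49 counts as Day 44.
- That the secondary objective rests on this endpoint alone. Time to first clearance serves it too and is unaffected.

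**Conclusion.** The censoring rule in SAP 6.2.2 is wrong as written for participants who withdraw or miss Day 44 while <LLOQ. It biases cumulative clearance downward and tends to make the median and quartiles late, even when loss is unrelated to outcome. That direction follows from the rule. The size depends on assumed clearance and dropout: at Day 15 the shortfall is about 2.5, 5 and 10 points for 5, 10 and 20% random loss.

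It would be tempting to report the gap of about 8 points between identical arms as the expected error. It needs a 5% vs 20% contrast in dropout that nothing in the documents suggests. At 5% vs 10% the gap is about 2.5 points, and both lie below one standard error at about 50 per arm. The consequence is a systematic distortion of one descriptive secondary curve. The primary endpoint is not affected by this rule. The correction is still worth making, because a reader of the curves could not detect the bias.

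**What to change.** In SAP 6.2.2, for a participant without a sustained event whose last available swab is <LLOQ, set the censoring date to the last visit with RNA >=LLOQ (baseline if none). Keep the current rule for all other non-events. State that this removes only part of the bias: at Day 15 with 20% loss the shortfall falls from 10.3 to 5.4 points, about half.

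Alongside it, report:
- the same curves restricted to participants with a Day 44 swab, noting that they are unbiased if loss is unrelated to outcome and too high if loss is concentrated in those still >=LLOQ;
- the number per arm censored while <LLOQ.

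The cost is a short SAP amendment and a small amount of programming on swabs already collected. The downside is earlier censoring and fewer participants at risk at later visits.
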